## Provisions to Monitor the Data to Ensure the Safety of Subjects

Adverse events will be monitored at each intervention visit. The PI and his co-investigators will review all data continuously to ensure the safety of each subject.

## Withdrawal of Subjects

Subjects may be withdrawn from the study if he/she misses study visits and will be notified of their withdrawal via telephone or mail. If a subject voluntarily withdraws from the study, no additional data will be collected and they will be considered dropouts in the study.

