### **Data analytic plan**

The biostatistics department will handle the randomization and use adaptive randomization to promote equal numbers of men and women in each cell and to promote similar BMI across the groups.

The primary outcome variable is body weight change, represented as kg and percent change. All other variables are secondary and will be analyzed using a similar statistical approach. Repeated mixed linear models will be used to determine if change in the outcome variables differs among the groups. Covariates will include the baseline value of the outcome, sex, and race. Additional variable selection in the models will be determined through model fit statistics such as AIC.

Two sources of body weight data are obtained – weights collected in the clinic at baseline and week 12, and weights collected at the 12 intervention sessions. Both sources of data will be analyzed, though the presence of only two clinic weights means that analysis of the clinic weights will be a completers' analysis. The weekly weight data, however, will be analyzed using an intent-to-treat approach, and all participants' data will be analyzed who have a weight from their first and at least one subsequent intervention visit. Sensitivity analysis will be conducted to determine how the two methods effects the results.

The primary models will be a mixed effect model that accounts for the correlation of the subject over time modeling. Least square means based on the estimates from the mixed effect model will be used to test for differences of weight change between groups. Normality of the responses will be checked based on the Shapiro-Wilk test. Heterogeneity of variance effects for genders for each of the treatments will be analyzed first as potential subgroups.

Hypothesis 1 will test if participants assigned to the diet that corresponded to their genotype lost more weight than those assigned to a diet inconsistent with their genotype.

- H1: Weight loss in Cells A and D (combined) in Table 1 was significantly larger than weight loss in Cells B and C (combined).

Hypothesis 2 will analyze the fat responders and carbohydrate responders separately.

- H2a: Fat responders lost more weight on the high-fat diet (Table 1, Cell A) vs. the high-carbohydrate diet (Cell B), and
- H2b: Carbohydrate responders lost more weight on the high-carbohydrate diet (Table 1, Cell D) vs. the high-fat diet (Cell C).

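### Withdrawing participants for missed visits, with no provision for later weights, risks avoidable and possibly informative loss of outcome data

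*Combined protocol and SAP*

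**What the plan says.** Withdrawal of Subjects contains two separate provisions. The first is at the study's discretion: "Subjects may be withdrawn from the study if he/she misses study visits". It gives no number of missed visits, names no decision-maker, and does not say whether weights are still sought afterwards. The second concerns people who leave of their own accord; for them, "no additional data will be collected and they will be considered dropouts in the study".

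The Data analytic plan describes two analyses of weight. For the clinic weights at baseline and week 12, "the presence of only two clinic weights means that analysis of the clinic weights will be a completers" analysis. For the session weights, "The weekly weight data, however, will be analyzed using an intent-to-treat approach", limited to participants "who have a weight from their first and at least one subsequent intervention visit". The model is stated as follows: "The primary models will be a mixed effect model that accounts for the correlation of the subject over time modeling". One sensitivity analysis is named: "Sensitivity analysis will be conducted to determine how the two methods effects the results".

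The Background section says that interventionists know the diet but not the genotype pattern. The Power analysis plans for data on up to 154 participants, which equals the enrolment ceiling under Table 1. No attrition rate or allowance appears anywhere.

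**The concern.** Attendance is a behaviour that follows randomisation. The sessions exist to help participants keep to their diet, so people who miss them may well be losing less weight. Withdrawing such a person from the study gives up weights that might still have been obtained, in particular at the week-12 clinic visit, although consent still stands.

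If one diet is harder to follow, the loss will be uneven between diets and the remaining clinic weights will over-represent adherent participants. The planned sensitivity analysis offers little protection. It compares two weight sources that both lose data through the same rule, so agreement between them would not show that the missing data are harmless. At stake are mainly the two within-responder contrasts, A vs B and C vs D, in the clinic-weight analysis.

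**Working it through.** **Inputs from the documents.** Target difference 2.0 kg, SD 2.8 kg, alpha 0.05 (sidedness not stated), stated power 0.80 for A vs B or C vs D (Power analysis). Cells A and B have 52 each and cells C and D have 25 each, in total 154 (Table 1).

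**Inputs that are assumptions.** Withdrawal differs by 10 percentage points between diets. Completers have lost 2 to 3 kg more than those withdrawn would have lost. The documents give neither figure.

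**Step 1: the plan's own power figure.** For a two-sample t-test the noncentrality is d divided by SD × √(2/n).
- 25 per cell: 2.0 divided by 2.8 × √(2/25) gives 2.53 on 48 df. Power is 0.801 one-sided and 0.697 two-sided.
- The stated 0.80 for C vs D is thus reproduced only with a one-sided test and complete data.
- 21 per cell (an assumed loss of 4 of 25): 2.0 divided by 2.8 × √(2/21) gives 2.31 on 40 df. Power is 0.736 one-sided and 0.617 two-sided.

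These power figures describe attrition from any cause. None of the loss can be assigned to this rule.

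**Step 2: bias in a completers' contrast.** Let p be the proportion withdrawn and δ the completer-minus-withdrawn difference in mean weight loss.
- Overall mean = (1 − p) × completer mean + p × withdrawn mean = completer mean − pδ.
- So completer mean = overall mean + pδ.
- With the same δ in both diets, bias of the contrast = (p₁ − p₂) × δ = 0.10 × 2 to 0.10 × 3 = 0.2 to 0.3 kg.
- Relative to the target of 2.0 kg, 0.2 kg is 10% and 0.3 kg is 15%.

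**Step 3: carry this to Hypothesis 1.** Suppose the high-fat diet has the higher withdrawal. Completers in A and C then both look too good. A minus B is inflated by 0.2 to 0.3 kg, and D minus C is reduced by the same amount. In the pooled contrast of A and D against B and C, weighted by planned cell sizes, most of this cancels. The net weight is 52 minus 25, which is 27, out of 52 plus 25, which is 77:
- 0.2 kg × 27/77 = 0.07 kg
- 0.3 kg × 27/77 = 0.11 kg

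That is about 4% to 5% of 2.0 kg. If the other diet has the higher withdrawal, the signs reverse.

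**Step 4: a second illustration, with the same dropout mechanism in both groups.** Completers were simulated with a true difference of 2.0 kg, SD 2.8, and odds of dropout rising by a factor of 1.2 to 1.5 for each kg less weight lost (assumed).

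| Overall dropout | Completers' difference (kg) |
|---|---|
| 10% | 1.95 to 1.83 |
| 20% | 1.92 to 1.74 |
| 30% | 1.90 to 1.67 |

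With no true difference and the same mechanism in both groups, the bias is about zero.

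**Step 5: which analysis is affected.** Steps 2 to 4 apply to the clinic-weight analysis. The weekly mixed model was not simulated. It uses partial records, so a participant removed after several sessions still contributes the weights recorded up to then.

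**The case against.** The strongest reply is that the rule does less than it first appears to.

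- It is permissive, and a person who misses visits already lacks those weights. Its added effect is limited to weights that person would have given later. This stands: the documents show a risk, not an established informative loss.
- A reader might infer that the protocol orders data collection to stop after a staff withdrawal. It does not. The explicit stop is written for voluntary withdrawal only. Being withdrawn from the study suggests the same outcome, but that is an inference.
- A reader might infer that the rule deletes outcome data and defeats the intent-to-treat analysis. Nothing already collected is removed, and the mixed model remains valid if missingness depends on observed weights and covariates. What remains is the loss of later weights, the exclusion of anyone removed before a second session weight, and exposure if missingness depends on unobserved weights.
- A reader might infer that unblinded staff could steer withdrawals in favour of the hypothesis. The text does not say that interventionists decide, and their blinding to genotype limits any steering by matched status.
- Virtual sessions make attendance easier, which may reduce the number affected.

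These points narrow the concern but do not remove it. Having missed some sessions is no reason to give up the remaining ones or the week-12 visit, and the data cannot verify that missingness depends only on what was observed.

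**Conclusion.** The concern holds as a risk that is cheap to avoid. As written, participants who still consent may be removed from the study for a post-randomisation behaviour, with no provision to keep seeking their weights. The clinic-weight analysis is the more exposed of the two because it depends on the week-12 value.

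The size cannot be determined from the documents. The shifts in steps 2 and 3 rest entirely on the assumed 10-point imbalance and 2 to 3 kg gap; they are modest within responder groups and small for Hypothesis 1. It would be wrong to read the fall in C vs D power as the effect of this rule. Whether the stated 0.80 was meant as one-sided is a separate question.

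**What to change.** Amend Withdrawal of Subjects so that missed intervention visits do not end outcome follow-up. Ask everyone who has not withdrawn consent for the week-12 clinic weight, analyse them in their randomised group, and record the reasons for missed visits. Voluntary withdrawal of consent stays as a separate, legitimate stop.

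If only a home-scale weight can be obtained at week 12, use it in a sensitivity analysis and do not pool it with the clinic weights. Home scales are participant-operated, a participant's own scale is calibrated at the baseline visit, and the plan gives no rule for combining the two sources.

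The cost is a short protocol change and some reminder calls. The week-12 visit is already scheduled, so no new procedure is needed.

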## Risks to Subjects

This study does not involve major risk to study participants.

- **Bioelectrical Impedance Analysis (BIA):** There is no known risk associated with the BIA measurement.
- **Blood Pressure Testing:** Temporary discomfort may be experienced during blood pressure recordings due to the pressure of the cuff inflating on their arm. No other known risks are associated with blood pressure testing.
- **Self-reported Questionnaires:** There are no anticipated risks from completing self-report questionnaires. Due to the sensitive nature of the questionnaires, participants may skip any questions that they do not wish to answer.
- **Blood collection:** The risks of taking blood include pain, a bruise at the point where the blood is taken, redness and swelling of the vein and infection, and a rare risk of fainting. Aseptic (sterile) technique and trained personnel minimize these risks.
- **Genetic Information:** As part of this study, Pennington Biomedical Research Center will analyze the results from the 23andMe, Ancestry.com or GeneticDirection genealogy test and work with participants' genetic information to determine if they are a carbohydrate or fat responder. All attempts will be made to maintain a subject's privacy. Safeguards such as password-protected computer and networks have been put in place in order to limit access to subject data.
- **Diet Risk:** There are no anticipated risks associated with the expected amount of weight loss during this study. The high carbohydrate diet is higher in carbohydrate and the high-fat diet is higher in fat than typical recommendations during weight maintenance. In the high-fat diet, expected dietary fat intake is about 11% percentage points higher than the typical American diet, but the proposed diet keeps saturated fat intake to less than 10%, which is consistent with guidelines. The high carbohydrate diet is about 22% higher than the typical American diet. There are limited anticipated risks of following such a high fat or high carbohydrate diet for 12 weeks, particularly when body weight is being reduced. The changes in dietary intake may lead to minor abdominal and bowel issues.
- **Information collected via 23andMe, Ancestry.com, and/or GeneticDirection:** Pennington Biomedical Research Center will create an online account for each participant, using a newly created email address ([POINTS\\[contact]](mailto:[contact]), [POINTS\\[contact]](mailto:[contact]), etc.) and the participant's date of birth. If a name and phone number are required for creating the online account, we will use POINTS\_01, POINTS\_02 etc. for the name and a Pennington phone number. Pennington Biomedical Research Center will have access to the login information during the study to retrieve the raw data once they are available. After completion of the study, the login information will be provided to each participant, which will give them access to their genealogy data.
  - Participants further have the option to provide additional information about themselves through surveys, forms, features, and applications. Unless they consent to sample storage ("Biobanking") and additional analyses, their saliva

sample and DNA are destroyed after the laboratory completes its work, subject to the laboratory's legal and regulatory requirements.

- 23andMe, Ancestry.com, and GeneticDirection give the ability to share information, including Personal Information, through their services related to health and ancestry. Participants have the option to share directly with individuals with via their accounts through (i) forums, (ii) relative finding features (e.g., "DNA Relatives"), and (iii) other sharing features and tools.
- Participants are advised to read the current version of the Privacy Statement for 23andMe, Ancestry.com or GeneticDirection provided as a link within the consent form to understand how these companies will use their information
  - <https://www.23andme.com/about/privacy/>
  - <https://www.ancestry.com/cs/legal/privacystatement>
  - <https://geneticdirection.com/privacy-policy/>
- Participants are made aware that for the purpose of this study, the collaborating institutions, but no one else, needs to receive their genetic information. Should they choose to provide additional information to 23andMe, Ancestry.com or GeneticDirection, have their samples stored by these companies, or share their genetic information with others, they do so at their own risk.

### **Potential Benefits to Subjects**

Participants will learn if they are a fat or carbohydrate responder and they are expected to lose weight, which conveys many health benefits. No further benefits can be promised.

### **Sharing of Results with Subjects**

The participants may receive information such as body weight, anthropometrics, and other health-related outcomes assessed during the study. Those results will be provided to the participant at the end of the study if requested.

### **Setting**

We will utilize the clinical facilities at PBRC to conduct this study. The dietary program and other intervention materials will be developed and administered by PBRC staff.

### **Compensation**

Participants will receive \$150 for successful completion of the study.

### **Provisions to Protect the Privacy Interests of Subjects**

All attempts will be made to maintain a subject's privacy. Safeguards such as password-protected computer and networks have been put in place in order to limit access to subject data. Subjects will be given ample time to read over the consent, ask questions, and agree to participate in the research study. Subjects may decline to answer questions they are not comfortable with. Each procedure will be explained to the subject before it is performed. We will always ensure the privacy of the subjects. Participants will attend group session and will, therefore, be known to other participants in the study. If you are participating in a virtual (online) visit, we ask you to *not* share the participation link with anyone else.

### **Compensation for Research-Related Injury**

No compensation will be provided for research-related injury.

### **Economic Burden to Subjects**

All study-related tests and procedures will be at no cost to the subject. The subject will incur transportation costs in getting to PBRC.

## Consent Process

The PI or one of the designated clinic staff will obtain informed consent in the PBRC clinic during the first visit. Ample opportunity will be given for the subject to review the consent and ask any questions prior to signing the consent form. If subjects wish, they can take the form home and return at a different visit. Also, as we are aware, consent is an ongoing process.

